9.4.2. Secondary Safety Analyses

9.4.2.1. Growth

Secondary analyses pertinent to growth will also include the following:

1. Summary of the proportion of children who are below the 3rd percentile of growth velocity

2. Summary of change (shift) in growth velocity quartile for each child from baseline to endpoint (definition of baseline and endpoint will be provided in the RAP)
3. Analysis of the first 12 weeks (~10 to 13 weeks given visit windows, Section 7.1) of data
4. Summary of growth velocities during the baseline and follow-up periods
5. Analysis of growth velocities for the following region subgroups: USA and Non-USA
6. Descriptive comparison of the growth velocities based on gender and ethnicity
7. Summary by visit and by treatment group of standard deviation scores and summary of change in height standard deviation scores from baseline to endpoint (definition of standard deviation scores, baseline and endpoint will be provided in the RAP)
8. Analysis of random coefficients

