5.2. Baseline Definitions

In general, the baseline study period will be defined as an aggregate of measurements recorded during the period between screening and randomisation (Visits 1 – 5). Specific details follow below.

Baseline growth velocity

Each participant's baseline growth velocity (cm/yr) will be calculated based on the stadiometric height measurements recorded at Visits 1, 3, and 5. These data will be used to fit a simple linear regression line against time. The slope of the fitted regression line will be the participant's baseline growth velocity. Note that baseline growth velocity will be derived if there are baseline stadiometric height assessments from at least two clinic visits. Otherwise baseline will be missing.

Baseline height standard deviation score (SDS)

Each participant's Visit 5 height standard deviation score will serve as the baseline height SDS. Height standard deviation scores will be calculated as described in Section 11.6.3.

Baseline eDiary measures

Baseline PEF will be defined as the average of the measurements recorded on the morning of randomisation (Visit 5) and on the previous 6 days.

The average daily rescue medication used over the last 7 days prior to randomisation, including the rescue medication use recorded on the morning of randomisation, will be used as the baseline value.

The baseline percentage of rescue-free 24-hour periods will be defined as the percentage of 24-hour periods in the 6 days prior to randomisation and on the day of randomisation in which a participant used no rescue medication. Percentage rescue-free 24-hour periods will be calculated as described in Section 11.6.5.

The baseline percentage of symptom-free 24-hour periods will be defined as the percentage of 24-hour periods in the 6 days prior to randomisation and on the day of randomisation for which a participant's daytime asthma symptom score and night-time symptom score is 0. Percentage symptom-free 24-hour periods will be calculated as described in Section 11.6.5.

Baseline C-ACT score

Each participant's Visit 5 C-ACT score will serve as the baseline score.

Derivations and handling of missing baseline data

If the baseline for an endpoint is missing it will not be imputed using a different time point or derivation but will remain missing. For example, if there is no C-ACT value available at Visit 5, then baseline C-ACT will be missing.

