7.2.6. Height Standard Deviation Scores

Height standard deviation scores will be summarized by treatment at each study visit. A box-plot illustrating the height standard deviation scores at each visit for the two treatment groups will also be provided. Details of the calculation of the height standard deviation scores can be found in Section 11.6.3. All available on- and off-treatment height data will be used.

The change from baseline (Visit 5) to endpoint (Visit 18, Week 52) in height standard deviation scores will also be summarized by treatment group. The endpoint value will be selected from available on- and off-treatment height data at Visit 18. Change from baseline will be defined as the difference between the value of the measure at the

timepoint of interest and the baseline. If either baseline or endpoint values are missing, then the change from baseline in height SDS will not be calculated.

No formal statistical analysis is planned.

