- Each participant’s endpoint growth velocity will be programmatically compared to the imported data using the participant’s age at endpoint (age at the last Visit included in the endpoint) and age in the imported data that is closest to the actual age of the participant to determine the participant’s endpoint growth velocity quartile.
- Shifts from baseline will be determined as follows:

Analysis category	Change from baseline
Increase	1Q to 2Q, 3Q or 4Q; 2Q to 3Q or 4Q; 3Q to 4Q
Decrease	4Q to 3Q, 2Q or 1Q; 3Q to 2Q or 1Q; 2Q to 1Q
No change	Same quartile at both baseline and endpoint
- Shifts from quartile to quartile, both increases and decreases, will be summarized by treatment group in terms of frequency and percentage of the treatment group.

Questionable Height Measurements

- Questionable height measurements will be defined as either of the following:
 1. Any measurement obtained at a visit that is at least 0.05 cm less than the smallest measurement obtained at the previous visit; or
 2. Any measurement obtained at a visit that is at least 0.20 cm larger than the largest measurement obtained at the previous visit with the following caveat: if a subsequent visit was conducted and the mean of that visit is \geq the mean of the visit in question, then the measurement is acceptable; if a subsequent visit was not conducted then the measurement will be considered questionable. A hypothetical example appears below:

Visit	Height Measurement 1	Height Measurement 2	Height Measurement 3
6	100.0 cm	100.0 cm	101.0 cm
7	160.0 cm	101.0 cm	102.0 cm
8	101.0 cm	101.0 cm	101.0 cm

According to the rules outlined above, measurement 1 at Visit 7 (160.0 cm) would be flagged as questionable, as it is more than 0.20 cm larger than the largest measurement recorded at Visit 6 (101.0 cm). Additionally, because the mean of the subsequent Visit 8 measurements, 101.0 cm, is not greater than the mean of the Visit 7 measurements (121.0 cm) the measurement of 160.0 cm is still flagged as questionable.

Height Standard Deviation Scores (SDS)

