
 • Each participant's standard deviation score for each of the three required stadiometric height measurements is calculated as: [observed height measurement – standard median height for age at Visit 1] / [(standard 95th height percentile for age at the visit – standard 5th height percentile for age at the visit) / (2 x 1.645)]. • The standard median, 95th percentile, and 5th percentile values will be obtained from standard tables available on the website of the Centers for Disease Control and Prevention (CDC) [Guidance for Industry Orally Inhaled and Intranasal Corticosteroids: Evaluation of the Effects on Growth in Children, 2007]. • The standard deviation scores for each height stadiometric measurement at each visit will be calculated using the CDC percentiles and will then be averaged for each participant before being summarized by treatment group.

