2.30.	Growth	Non-Standard GRO_T1	Summary of Growth Velocity (cm/yr) by Region	Using all available on- and off-treatment height data. (US and non-US sites)	SAC
2.31.	Growth	Non-Standard GRO_T2	Analysis of Growth Velocity (cm/yr) by Region	Using all available on- and off-treatment height data. (US and non-US sites)	SAC

Safety Tables					
No.	Population	GSK Standard / Example Shell	Title	Programming Notes	Deliverable [Priority]
2.32.	Growth	Non-Standard GRO_T1	Summary of Growth Velocity (cm/yr) by Gender	Using all available on- and off-treatment height data and including Summary of Change from Baseline.	SAC
2.33.	Growth	Non-Standard GRO_T1	Summary of Growth Velocity (cm/yr) by Ethnicity	Using all available on- and off-treatment height data and including Summary of Change from Baseline.	SAC
2.34.	Growth	Non-Standard GRO_T6	Summary of Height Standard Deviation Scores	Using all available on- and off-treatment height data.	SAC
2.35.	Growth	Non-Standard GRO_T7	Summary of Change in Height Standard Deviation Scores from Baseline to Endpoint	Similar to summary of C-ACT scores.	SAC
2.36.	Growth	Non-Standard GRO_T8	Analysis of Growth Velocity (cm/yr) using Random Coefficients	Using all available on- and off-treatment height data.	SAC
Adverse Events (AEs)					
2.37.	ITT	AE13	Adverse Events Overview	By epoch: pre-treatment, on-treatment, and post-treatment.	SAC
2.38.	ITT	AE1	Summary of Pre-Treatment Adverse Events		SAC
2.39.	ITT	AE1	Summary of On-Treatment Adverse Events		SAC
2.40.	ITT	PAN10	Summary of On-Treatment Adverse Events Over the Time Course of the Trial (Pre, During, and Post Pandemic)	Use IDSL PAN10 shell	SAC
2.41.	ITT	AE1	Summary of Post-Treatment Adverse Events		SAC

Safety Tables					
No.	Population	GSK Standard / Example Shell	Title	Programming Notes	Deliverable [Priority]
2.42.	ITT	AE1	Summary of Drug-Related Adverse Events		SAC
2.43.	ITT	AE1	Summary of Adverse Events Leading to Permanent Discontinuation of Study Treatment or Withdrawal from Study		SAC
2.44.	ITT	AE3	Summary of Common ($\geq 3\%$) On-Treatment Adverse Events by Overall Frequency		SAC
2.45.	ITT	AE15	Summary of Common ($\geq 3\%$) On-Treatment Non-serious Adverse Events (Number of Subjects and Occurrences)	FDAAA, EudraCT	SAC
2.46.	ITT	AE3	Summary of Non-Serious Drug-Related Adverse Events by Overall Frequency	Plain Language Summary requirements.	SAC
Serious and Other Significant Adverse Events					
2.47.	ITT	AE1	Summary of Pre-Treatment Serious Adverse Events		SAC

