11.9.7. Safety Figures

Safety: Figures					
No.	Population	GSK Standard / Example Shell	Title	Programming Notes	Deliverable [Priority]
2.1.	Growth	Non-Standard GRO_F1	Height Standard Deviation Scores	Boxplot of Standard Deviation Scores using all available on- and off- treatment height data.	SAC
2.2.	Growth	Non-Standard GRO_F2	Growth Velocity (cm/yr) Over the Double-Blind Treatment Period	Histograms by treatment.	SAC
2.3.	Growth	Non-Standard GRO_F3	Distribution of Double-Blind Treatment vs Baseline Growth Velocity Using On- and Off-Treatment Height Measurements – Growth Population	Scatter plot of baseline growth velocity vs growth velocity during double-blind treatment period using all available on- and off-treatment data.	SAC
2.4.	ITT	Non-Standard GRO_F3	Distribution of Double-Blind Treatment vs Baseline Growth Velocity Using On- and Off-Treatment Height Measurements – Intent-to-Treat	Scatter plot of baseline growth velocity vs growth velocity during double-blind treatment period using all available on- and off-treatment data.	SAC
2.5.	Growth	Non-Standard GRO_F3	Distribution of Double-Blind Treatment vs Baseline Growth Velocity Using On-Treatment Height Measurements – Growth Population	Scatter plot of baseline growth velocity vs growth velocity during double-blind treatment period using only available on-treatment data.	SAC

Safety: Figures					
No.	Population	GSK Standard / Example Shell	Title	Programming Notes	Deliverable [Priority]
2.6.	Growth	Non-Standard GRO_F3	Distribution of Double-Blind Treatment vs Baseline Growth Velocity Excluding Subjects with Tanner Stage ≥ 2	Scatter plot of baseline growth velocity vs growth velocity during double-blind treatment period using only available on-treatment data.	SAC
2.7.	Growth	Non-Standard GRO_F3	Distribution of Double Blind Treatment vs Baseline Growth Velocity Excluding Questionable Height Measurements	Scatter plot of baseline growth velocity vs growth velocity during double-blind treatment period using only available on-treatment data.	SAC
2.8.	Growth	Non-Standard GRO_F3	Distribution of Double Blind Treatment vs Baseline Growth Velocity Excluding Height Measurements Taken after Receiving Rescue Systemic Corticosteroids	Scatter plot of baseline growth velocity vs growth velocity during double-blind treatment period using only available on-treatment data.	SAC

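### The height SDS formula fixes the reference median at age at Visit 1 but takes the reference spread at current age, so ordinary growth would show as a false rise of about 1 SDS in both arms

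*SAP*

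**What the plan says.** Height SDS at each visit is a listed secondary endpoint (Protocol 3; SAP 2.2). Protocol 9.4.2.1 leaves the detail to the SAP: "definition of standard deviation scores, baseline and endpoint will be provided in the RAP". The definition is in SAP 11.6.3:

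- **Numerator:** observed height minus the "standard median height for age at Visit 1".
- **Denominator:** the 95th percentile for age at the visit minus the "standard 5th height percentile for age at the visit", divided by 2 x 1.645.
- **Reference values:** CDC tables, which neither document reproduces.

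SAP 5.2 sets the baseline: each participant's Visit 5 "height standard deviation score will serve as the baseline height SDS". SAP 7.2.6 plans a summary and a box-plot by visit, and adds: "The change from baseline (Visit 5) to endpoint (Visit 18, Week 52) in height standard deviation scores will also be summarized by treatment group". It plans no formal statistical analysis of SDS. The outputs are Table 2.34 (by visit), Table 2.35 ("Summary of Change in Height Standard Deviation Scores from Baseline to Endpoint") and Figure 2.1 ("Boxplot of Standard Deviation Scores using all available on- and off- treatment height data").

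**The concern.** An SDS is meant to place a child among peers of the same age, so the median and the spread must refer to the same age. Here the spread moves with age and the median does not. The two agree only at Visit 1. By the SAP schedule the median is 16 weeks out of date at Visit 5 and 68 weeks out of date at Visit 18.

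Nothing in the SAP suggests a purpose for a fixed median. Table 1 of the SAP, which lists changes from the protocol, does not mention one. The growth-velocity quartile derivation in the same section uses current age at the end of treatment: "age at endpoint (age at the last Visit included in the endpoint".

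The risk is a misleading display in a growth-safety study. An arm that truly loses height relative to its peers would be tabulated as having gained, and the distorted quantities are the ones planned for reporting.

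**Working it through.** **1. The plan's own constant.** The 95th percentile of the standard normal is 1.6449, which rounds to the SAP's 1.645. The 5th-to-95th percentile range divided by 2 x 1.645 is therefore the reference SD, and the denominator is sound.

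**2. Algebra.** Let M(t) and S(t) be the reference median and SD at the child's age at time t. A child who stays on a fixed centile z has height M(t) + z x S(t).

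- Printed formula: SDS(t) = z + [M(t) - M(Visit 1)] / S(t)
- Median at current age: SDS(t) = z at every visit

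The extra term is normal growth since Visit 1, expressed in SD units.

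**3. Inputs.**

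- Timing (SAP Appendix 2): Visit 1 at week -16, Visit 5 at week 0, Visit 18 at week 52.
- Reference growth: 5.74 to 5.94 cm/yr. These are means of ICS-treated school-aged groups cited in Protocol 2.2, used as a stand-in for CDC growth.
- Reference SD: 4.5 to 6 cm, assumed and held constant between visits.

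**4. False SDS = velocity x elapsed years / SD.**

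| Quantity | Years | Low | High |
|---|---|---|---|
| Visit 5 | 16/52 = 0.3077 | 5.74 x 0.3077 / 6 = 0.29 | 5.94 x 0.3077 / 4.5 = 0.41 |
| Visit 18 | 68/52 = 1.3077 | 5.74 x 1.3077 / 6 = 1.25 | 5.94 x 1.3077 / 4.5 = 1.73 |
| Change, Visit 5 to 18 | 52/52 = 1 | 5.74 / 6 = 0.96 | 5.94 / 4.5 = 1.32 |

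**5. Sensitivity of the change to the assumptions.**

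- SD widening by 0.28 cm/yr from the same starting values. Low end: 7.506/6.366 - 1.766/6.086 = 0.89. High end: 7.768/4.866 - 1.828/4.586 = 1.20.
- SD of 4.5 to 6.5 cm, widening by 0 to 0.3 cm/yr: 0.82 to 1.32.
- The same SD range with growth of 5.0 to 6.5 cm/yr: 0.71 to 1.44.

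**6. Scale.** The cited average ICS effect is a loss of 0.48 cm/yr (Protocol 2.1), which is 0.48/6 = 0.08 to 0.48/4.5 = 0.11 SDS over a year. With a constant SD the artefact is 5.74/0.48, about 12 times that effect, whatever the SD.

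**7. Effect on the comparison of arms.** Simulation of 20,000 trials. Inputs from the documents: 203 children per arm, SD of one-year growth 1.2 cm, and a loss of 0.48 cm/yr on FF. Assumed: 55% boys, ages uniform over the eligible ranges, reference growth of 6.2 cm/yr at age 5 falling by 0.14 per year of age, and reference SD of 4.6 cm at age 5 rising by 0.28 per year of age.

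| | As written | Median at current age |
|---|---|---|
| Placebo change | +1.06 | 0.00 |
| FF change | +0.97 | -0.09 |
| FF minus placebo | -0.088 | -0.088 |
| Sampling SD of the difference | 0.023 | 0.022 |

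The false term depends on age and sex, not on treatment. It cancels between arms in expectation and adds only a little noise.

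**The case against.** The strongest reply is that Visit 1 is a slip for the visit, the wording used in the other two terms of the formula, and that a programmer would see this. That is probably so, and the false rise appears only if the formula is coded literally. It remains the only definition in the text of either document, and correct output should not depend on a programmer overriding it. The mock shells (SAP Appendix 10) were not available for this check, so a correcting footnote there cannot be ruled out.

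A second reply is that the size rests on figures the documents do not give. This stands. The range with a constant SD is also somewhat narrow: allowing the SD to widen with age moves the lower end to 0.8 or 0.9. The order of magnitude survives every variation tried.

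Third, the per-visit figures assume exact age at Visit 1, while SAP 11.6.2 calculates age at screening in whole years. If that variable supplied the median, the simulation model gives average offsets of about +0.92 at Visit 5 and +1.95 at Visit 18. The change is about +1.03, so it is robust to this choice but the levels are not.

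Finally, the comparison of arms is unbiased, SDS is descriptive, and the primary analysis uses raw height. All of this is right, and it limits the seriousness of the point. But SAP 7.2.6 specifies no FF-minus-placebo SDS estimate, so readers would have to subtract the two arm means themselves to recover the undistorted quantity.

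**Conclusion.** The concern holds. As written, the formula mixes two ages and would turn a year of normal growth into a rise of about 1 SDS in each arm. The Visit 5 to Visit 18 change is 0.96 to 1.32 under the stated assumptions, and about 0.8 to 1.3 if the reference SD may be larger or widen with age. The mismatch and the direction of the error follow from the text alone. The size depends on assumed reference growth and spread.

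The damage is to readability. Tables 2.34 and 2.35 and Figure 2.1 would not show height for age, and a small true loss on FF would appear as a large gain. The point should be fixed, but it does not threaten the trial's main conclusion.

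**What to change.** In the SDS formula of SAP 11.6.3, take the standard median height for age at the visit, so that the median and both percentiles refer to the same age.

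As a separate clarification, add one sentence stating that age at each visit for this calculation is derived from the birth date that SAP 11.6.2 builds from the collected month and year. The only age derivation spelled out there is whole years at screening, although the quartile and 3rd-percentile derivations already rely on age at later visits.

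The cost is one phrase and one sentence. No new data are needed, and no other analysis changes.

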11.6.4. Safety

Adverse Events
General
Adverse events will be coded using the current MedDRA coding dictionary at the time of reporting providing a Preferred Term (PT) and a System Organ Class (SOC) for analysis and reporting.
AEs of Special Interest

 • The AEs of special interest are defined as AEs which have specified areas of interest for FF. • The adverse events of special interest groups, their subgroups and the PTs which will be counted towards each of them (groups and subgroups) will be based on the current version of MedDRA at the time of reporting and will be finalized prior to unblinding the study. • These AEs of special interest terms will be agreed prior to unblinding of the study and provided in a reference dataset for use in the specific summary tables. All special interest terms from the reference datasets will be listed.
Risks Plot

 • Relative risks and corresponding 95% CIs will be calculated as follows (Altman, 2005): • Relative risk = $(A/(A+C))/(B/(B+D))$ where A = number of participants with event of interest in the FF treatment group B = number of participants with event of interest in the placebo treatment group C = number of participants without event of interest in the FF treatment group D = number of participants without event of interest in the placebo treatment group. • Standard Error(log relative risk) (SElogR) = square root of $((1/A)-(1/(A+C))+(1/B)-(1/(B+D)))$ • 95% CI lower limit = exponential of $(\log(\text{relative risk}) - (\text{probit}(0.975)*SElogR))$ • 95% CI upper limit = exponential of $(\log(\text{relative risk}) + (\text{probit}(0.975)*SElogR))$ • Relative risks and 95% CIs will not be calculated if either or both treatment groups have no events of interest.

11.6.5. Efficacy

eDiary
Rescue-Free 24-Hour Periods

 Rescue medication use over the previous 24 hours is recorded in the eDiary each morning. Therefore, rescue medication use recorded on study day n refers to actual use on study day $(n - 1)$. A given 24-hour period will only be set to “rescue free” if responses to the daily assessment of rescue medication use is 0. Any >0 values will require that the 24-hour period be marked as not rescue-free. If the assessment of rescue medication use in a given 24-hour period is missing, then the “rescue-free” indicator will also be set to missing. Percentages of rescue-free 24-hour periods are calculated as the number of 24-hour periods on which a participant recorded no use of albuterol/salbutamol divided by the length of the time period being assessed (with non-missing values of rescue medication recorded) x 100. See Section 11.7.2 for determination of rescue-free 24-hour periods and handling of missing data.
Symptom-Free 24-Hour Periods

 Daytime symptoms, reflective of the participant’s state during the previous day, are collected in the morning. Similarly, overnight symptoms are recorded the following morning. Therefore, daytime and nighttime symptoms recorded on study day n refer to the participant’s symptoms on study day $(n - 1)$. A given 24-hour period will only be set to “symptom free” for a given 24-hour period if responses to both the morning and evening asthma symptom scores are 0. Any >0 values in either the morning or evening assessment will require that the 24-hour period be marked as not symptom-free. If either the morning or evening assessment asthma symptom score in a given 24-hour period is missing, then the “symptom-free” indicator will also be set to missing. Percentages of symptom-free 24-hour periods are calculated as the number of 24-hour periods on which a participant recorded no symptoms divided by the length of the time period being assessed (with non-missing values of symptoms recorded) x 100. See Section 11.7.2 for determination of symptom-free 24-hour periods and handling of missing data.
Peak Expiratory Flow (PEF)
Peak expiratory flow (PEF) is recorded in the morning, thus a PEF measurement recorded on study day n is associated with study day n .

11.7. Appendix 7: Reporting Standards for Missing Data

11.7.1. Premature Withdrawals

Element	Reporting Detail
General	
 • A completed participant is one who has completed all phases of the study (as specified in the protocol) including the follow-up visits. • Participants who withdrew prematurely either from study treatment or from the study itself will not be replaced. • All available data from participants who were withdrawn from study treatment (i.e., double-blind treatment) or from the study will be listed and where possible any available data from withdrawn participants will be included in summaries or analyses, unless otherwise specified.

